6.1. Study Entry/Screening Period (Visit 1)

Visit 1 and Visit 2 can occur up to 28 days apart. All Screening Period procedures should be performed as per Table 1.

Informed Consent/Previous Participation: The initial screening visit will occur up to 28 days prior to the initial administration of IP. Before or at Visit 1, qualified site personnel will explain the study to the subject, answer all of his/her questions, and obtain written informed consent/ Health Insurance Portability and Accountability Act (HIPAA) authorization before performing any study-related procedures. A copy of the signed informed consent will be given to the subject, and the date of the signing of the informed consent will be recorded in the electronic case report form (eCRF) and in the source documents. Previous participation in any other CCT-PDA study will be recorded in the eCRF and in the source documents.

Assessment of Adverse Events: Adverse events (AEs) will be collected from the time the subject signs the informed consent throughout the study. The type, frequency and severity of adverse events and potential relationship to IP will be collected as described in the full study protocol.

Demographics/Medical and Surgical History: Demographics and medical history will be obtained during screening. Demographics will include subject's initials, date of birth, sex, ethnicity, and race. A thorough medical and surgical history including date of diagnosis of DM and DPN, psychiatric conditions, current medical conditions, and any known allergies will be performed.

Prior/Concomitant Medications: All medications taken (including contraception measures) within the last **35 days** should be recorded. All medications that a subject is currently taking will also be recorded from the time the subject signs the informed consent throughout the study.

Physical Examination/Vital Signs: Subjects will undergo a routine physical examination.

Vital signs including height (cm) (Visit 1 only), weight, (kg) body temperature (°C), pulse (beats/minute), respiration (breaths/minute), and resting systolic and diastolic blood pressure (mmHg) will be measured and recorded in the eCRF and in the source documents.

Pregnancy Testing

Serum pregnancy testing at Screening and urine pregnancy testing at all other visits of females of childbearing potential. At Visit 2 a urine pregnancy needs to be performed if a serum pregnancy test was not done within 0-72 hours predose. Pregnancy testing will be conducted prior to treatment on Study Days 1, 29, and 57.

Electrocardiogram: A 12-lead ECG will be obtained. At screening, if a 12-lead ECG was performed as part of the subject's previous routine care within 28 days prior to signing of the informed consent, it does not need to be repeated. The following will be recorded in the eCRF and in the source documents:

Any ECG finding that is judged by the investigator as a clinically significant change (worsening) compared to a baseline value will be considered an AE and will be recorded and monitored.

Clinical Laboratory Tests: Blood and urine samples for routine laboratory testing as well as blood for exploratory biomarker analysis will be obtained as per the Table of Events (Table 1) and will be evaluated by a central laboratory. Please refer to the Laboratory Manual for detailed information on the collection, storage, and shipment of laboratory samples.

Serum Chemistry

Serum chemistry will be assessed at all visits as indicated in the Table of Events (Table 1) and will include the following:

- Calcium
- Chloride
- Potassium
- Sodium
- Phosphorus
- Uric acid
- Alanine Aminotransferase (ALT; SGPT)
- Aspartate Aminotransferase (AST; SGOT)
- Creatinine
- Blood Urea Nitrogen (BUN)

Hematology

Hematology tests will be performed at all visits as indicated in the Table of Events (Table 1) and will include the following:

- Hemoglobin
- Red Blood Cell (RBC) Count
- Absolute Neutrophil Count (ANC)

- Total Bilirubin
- Indirect Bilirubin
- Direct Bilirubin
- Glucose
- Bicarbonate or Carbon Dioxide
- Lactic Dehydrogenase (LDH)
- Alkaline Phosphatase (ALK)
- Total Protein
- Albumin

- Hematocrit
- Platelet Count
- White Blood Cell (WBC) Count and Differential Count

Urinalysis

Urinalysis will be performed at visits indicated in the Table of Events (Table 1) and will include the following:

Urine albumin and creatinine to be collect with the morning void

- Protein
- Ketones
- pH
- Microscopic (if gross findings are positive, then a microscopic examination, including WBCs/high power field (HPF) and RBCs/HPF, will be performed).
- Glucose
- Blood (hemoglobin)
- Specific Gravity
- Bilirubin
- Urinary Albumin
- Creatinine

• Leukocyte Esterase

Immunological/Inflammation Assessments

Immunological/inflammation assessment will include the following testing:

• Anti-HLA antibodies as indicated in the Table of Events (Table 1).

Hemoglobin A1c

Hemoglobin A1c will be measured as indicated in the Table of Events (Table 1).

Coagulation Tests

Coagulation tests including assessment of PT/PTT, D-dimers, fibrinogen, and platelets will be assessed as indicated in the Table of Events (Table 1) prior to dosing with IP and approximately 2 hours post-dose. Assessments can be performed within 1 hour of the 2 hour post dose time frame.

Tryptase and Histamine

Tryptase and histamine levels will be assessed on the day of treatment prior to dosing with IP and approximately 2 hours postdose as indicated in the Table of Events (Table 1).

Exploratory Biomarkers

Exploratory biomarkers will be measured as indicated in the Table of Events (Table 1).

Skin Biopsies: Two 3mm thickness skin punch biopsies will be taken at the lateral aspect of the distal legs (2 biopsies; 1 per leg) approximately 10 cm above the lateral malleolus, and two biopsies will be taken at the volar aspect of the forearm (2 biopsies on 1 forearm). Instructions for tissue collection, handling, and shipping instructions are located in the Laboratory Manual.

Contraception: Females of childbearing potential¹ must use adequate contraception for the duration of their participation in the study (which includes 28 days prior to starting IP, during the Treatment Period [including dose interruptions], and during the Follow-up Period). Adequate contraception is defined as the simultaneous use of 2 of the following forms of contraception methods: oral, injectable or implantable hormonal contraception; tubal ligation; intrauterine device (IUD); barrier contraceptive with spermicide; or a vasectomized partner.

Males (including those who have had a vasectomy) must agree to use barrier contraception (latex condoms) when engaging in sexual activity with females of child bearing potential (FCBP) for the duration of their participation in the study, including the Follow-up Period.

Retinal Assessment: Retinal assessment conducted by an ophthalmologist or optometrist will be performed and scored using the International Clinical Diabetic Retinopathy Disease Severity Scale (Appendix B). Results will be recorded in the eCRF and in the source documents.

6-Item Neuropathy Total Symptom Score (NTSS-6): To be completed as outlined in Efficacy Procedures Section 6.4.

Neurological Impairment Score of the Lower Limb (NIS-LL): To be completed as outlined in Efficacy Procedures Section 6.4.

Utah Early Neuropathy Scale (UENS): To be completed as outlined in Efficacy Procedures Section 6.4.

Nerve Conduction Studies: To be completed as outlined in Efficacy Procedures Section 6.4.

Quantitative Sudomotor Axon Reflex Testing (QSART): To be completed as outlined in Efficacy Procedures Section 6.4.

Norfolk QOL-DN: To be completed as outlined in Efficacy Procedures Section 6.4.

Patient Global Impression of Change in Neuropathy (PGICN): To be assessed as outlined in Efficacy Procedures Section 6.4.

Vascular Reactivity Measurements*: To be completed as outlined in Efficacy Procedures Section 6.4.

*This procedure will only be measured if it is available for this study protocol at the participating site.

Hyperspectral Imaging (HSI)*: To be completed as outlined in Efficacy Procedures Section 6.4.

* This procedure will only be performed if it is available for this study protocol at the participating site.

Final Review of All Inclusion/Exclusion Criteria: The investigator or designee will review all inclusion/exclusion criteria once the subject has completed all screening assessments. If the subject meets all of the study entrance criteria, the subject will be randomized and scheduled for dosing with IP. Study site personnel will contact the Interactive Web Response System (IWRS)

¹ A female of childbearing potential is a sexually mature female who 1) has not undergone a hysterectomy (the surgical removal of the uterus) or bilateral oophorectomy (the surgical removal of both ovaries) or 2) has not been postmenopausal for at least 24 consecutive months (ie, has had menses at any time during the preceding 24 consecutive months). Tubal ligation is not sufficient for non-child bearing potential.

for each subject's treatment group assignment, and the randomization number will be recorded in the eCRF and in the source documents.

6.2. Treatment Period (Visit 2 through Visit 9)

Visit 2 through Visit 9 should occur on the days specified within the allowable variance. All Treatment Period procedures should be performed as per Table 1.

Administration of IP (Visit 2, Visit 4, and Visit 5)

IP will be administered on Study Days 1, 29 and 57. Preparation and administration of IP is discussed in Section 8.2.

IP Administration Information: IP thaw time, start and stop time of injections, and administration interruption/completion will be recorded in the eCRF and in the source documents.

IP Administration Vital Signs: Vital signs including heart rate, respiration, blood pressure, and body temperature will be monitored prior to starting the injections and at 1 and 2 hours after completion of the injections (\pm 15 minutes).

IP Administration Additional Blood Sampling: Blood samples for tryptase and histamine, coagulation assessments (PT/PTT), and exploratory biomarkers will be collected 2 hours before (\pm 15 minutes) IP administration and also at 2 hours after IP administration for tryptase and histamine assessments as indicated in the Table of Events (Table 1).

IP Administration Adverse Event Monitoring: A visual inspection of injection sites will be conducted periodically from the initial injection until 2 hours after the last injection (minimum). Any clinically significant findings will be recorded as AEs in the eCRF and in the source documents.

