Quantitative Sudomotor Axon Reflex Testing (QSART)	Х	-	-	-	-	-	-	-	Х	-	-	Х	-	Х			
Skin biopsies	Х	-	-	-	-	Х	-	-	Х	-	-	-	-	-			
Histology of Immune Cells (mast cell)	Х	-	-	-	-	Х	-	-	Х	-	-	-	-	-			
Norfolk Quality of Life Assessment (Norfolk-QOL-DN)	Х	-	-	-	-	Х	-	-	Х	-	-	Х	-	Х			
Patient Global Impression of Change in Neuropathy (PGICN)	X	Х	Х	X	X	-	-	-	Х	-	-	X	-	X			

	Screening Period	Treatment Period				Follow-up Period								
	V1	V2	V3	V4	V5	V6	V7	V8	V9	V10	V11	V12	V13	
	Day -28 to Day 0	Day 1 (±3 days)	Day 15 (±3 days)	Day 29 (±3 days)	Day 57 (±3 days)	Day 93 (±7 days)	Day 120 (±3 days)	Day 155 (±3 days)	Day 186 (±7 days)	Day 246 (±7 days)	Day 306 (±7 days)	Day 365 (±7 days)	Day 425 (±7 days)	Early Termin- ation
Event		Week 1	Week 2	Month 1	Month 2	Month 3	Month 4	Month 5	Month 6	Month 8	Month 10	Month 12	Month 14	
Vascular reactivity measurements- (including Laser Doppler Iontophoresis and Nerve Axon Reflex measurements)	Х	-	-	-	-	Х	-	-	Х	-	-	Х	-	-
Administration of IP	-	Х	-	Х	Х	-	-	-	-	-	-	-	-	-
IP administration monitoring (including visual inspection of injection areas, vital signs, and collection of blood for coagulation tests and tryptase/histamine evaluation before and after IP administration)	-	Х	-	х	х	-	-	-	-	-	-	-	-	-
Assess and record adverse events ^d	Х	Х	Х	Х	Х	Х	Х	Х	Х	Х	Х	Х	X	Х

Table 1:Table of Events (Continued)

Abbreviations: IP=Investigational Product, PBMC=peripheral blood mononuclear cell, RBC=red blood cell, SAE=serious adverse event.

^a Physical exams during the Screening Period and Early Termination will be full physical examinations. At all other assessments, physical examinations should only be directed to evaluate reported adverse events. Assessments for vital signs can be performed within15 minutes for the 1 and 2 hour post dose assessments.

^b Biomarkers assessed at Screening, Visit 2 Day 1 and Visit 4 Day 29, and Visit 5 Day 57 prior to injection of IP. Biomarkers will also be assessed on Day 93 when there is no IP injection. Biomarker samples will include blood immune biomarkers and RBC-lysed PBMC sample for the chip cytometry assay. The chip cytometry assay will only be performed at selected sites.

^c Serum pregnancy testing at Screening and urine pregnancy testing at all other visits of females of childbearing potential. At Visit 2 a urine pregnancy needs to be performed if a serum pregnancy test was not done within 0-72 hours predose. Prior to treatment on Study Days 1, 29, and 57.

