6.5. Safety

Safety will be assessed by an ongoing review of clinical laboratory tests (hematology, serum chemistry, coagulation, pregnancy, urinalysis, physical examination results, vital sign measurements, 12-lead ECG at screening only, weight, use of concomitant medications/procedures, and the incidence and severity of injection site and injection-related reactions (including tryptase and histamine) and treatment-emergent AEs.

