8.2. Treatment Administration and Schedule

Investigational product (IP) will be administered on Study Days 1, 29 and 57. Thawing of the IP should not begin until it is confirmed that the subject meets the inclusion/exclusion criteria. Investigational product thawing will be performed by qualified site personnel according to the instructions in Appendix E. Three 3 mL syringes will each be filled with 1.5 mL of IP, and then capped. Syringes will be masked to preserve blinding, and transferred to the personnel administering the injections.

Subjects will receive IP administered as fifteen 0.30 mL injections (approximately 4.5 mL total) in one leg. The target region is suggested to be below the knee and above the ankle. Injections are suggested to be at least 1 cm apart horizontally and laterally and at a depth of approximately 1 to 4 cm. It is suggested that they be administered in a pattern of 3 x 5 injections around the leg, and injections should not be near a blood vessel. The administrator will be blinded to treatment.

PDA-002 is not intended for intravenous administration. When the injection is given, the syringe should be aspirated to avoid inadvertent venous administration. If any blood is aspirated into the syringe, the needle is to be pulled out a little, and the syringe re-aspirated. If no blood is seen, the IP may be injected.

Vital signs (including heart rate, respiration, blood pressure, body temperature) will be monitored prior to starting the injections and at 1 and 2 hours (\pm 15 minutes) after completion of

the injections. Blood samples for tryptase and histamine, coagulation assessments, and exploratory biomarkers will be collected as indicated in the Table of Events (Table 1).

The investigational centers must also offer appropriate supplemental services that support clinical care to ensure that the protocol specified IP administration and monitoring will be followed.

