10.7. Safety Analysis

The safety analyses will be conducted using the Safety Population (all subjects who receive any amount of IP). Adverse events, vital sign measurements, physical examination findings, clinical laboratory test results, injection site assessments, retinal assessment results, ECG interpretations, and concomitant medications and procedures will be tabulated and summarized as appropriate.

Adverse events observed will be classified using the Medical Dictionary for Regulatory Activities (MedDRA) classification system. If clinically significant, any or all laboratory evaluations should be reported as AEs and repeated more frequently, if clinically indicated. The severity of the toxicities will be graded according to the National Cancer Institute (NCI) Common Terminology Criteria for Adverse Events (CTCAE) Version 4.03 whenever possible.

The frequency of AEs will be tabulated by MedDRA system organ class and preferred term. In the by-subject analysis, a subject having the same event more than once will be counted only

once. Adverse events will be summarized by NCI CTCAE grade. Adverse events leading to discontinuation from treatment, events classified as NCI CTCAE Grade 3 or higher, study-drug-related events, and SAEs will be tabulated and listed separately. By-subject listings of all AEs, SAEs, discontinuations due to AEs, and deaths will be provided.

Clinical laboratory data will be summarized. Laboratory data will be graded according to NCI CTCAE Version 4.03 criteria wherever possible. The frequencies of the worst severity grade observed during treatment will be displayed in cross-tabulations by screening status.

Vital signs, ECG, and retinal examination data will be summarized by cross-tabulations presenting normal and abnormal values.

Graphical displays will be provided where useful in the interpretation of results.

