11. ADVERSE EVENTS

11.1. Monitoring, Recording and Reporting of Adverse Events

An AE is any noxious, unintended, or untoward medical occurrence that may appear or worsen in a subject during the course of a study. It may be a new intercurrent illness, a worsening concomitant illness, an injury, or any concomitant impairment of the subject's health, including laboratory test values (as specified by the criteria in Section 11.3), regardless of etiology. Any worsening (ie, any clinically significant adverse change in the frequency or intensity of a preexisting condition) should be considered an AE. A diagnosis or syndrome should be recorded on the AE page of the eCRF rather than the individual signs or symptoms of the diagnosis or syndrome.

Abuse, withdrawal, sensitivity or toxicity to an investigational product should be reported as an AE. Overdose, accidental or intentional, whether or not it is associated with an AE should be reported on the overdose CRF. See Section 8.2.2 for the definition of overdose. Any sequela of an accidental or intentional overdose of an investigational product should be reported as an AE on the AE eCRF. In previous studies doses that were one half log greater than the highest dose in this study were not associated with any drug related adverse events. If the sequela of an overdose is an SAE, then the sequela must be reported on an SAE report form and on the AE eCRF. The overdose resulting in the SAE should be identified as the cause of the event on the SAE report form and eCRF but should not be reported as an SAE itself.

In the event of overdose, the subject should be monitored as appropriate and should receive supportive measures as necessary. There is no known specific antidote for PDA-002 overdose. Actual treatment should depend on the severity of the clinical situation and the judgment and experience of the treating physician.

All subjects will be monitored for AEs during the study. Assessments may include monitoring of any or all of the following parameters: the subject's clinical symptoms, laboratory, pathological, radiological or surgical findings, physical examination findings, or findings from other tests and/or procedures.

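### Section 6.2 names only clinically significant injection-site findings for recording, which is narrower than 11.1 and 11.2.2, so mild reactions to 45 injections per subject risk being under-counted in the outputs of 6.5 and 10.7

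*Combined protocol and SAP*

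**What the plan says.** **Exposure.** Section 8.2: "Subjects will receive IP administered as fifteen 0.30 mL injections (approximately 4.5 mL total) in one leg". Section 6.2: "IP will be administered on Study Days 1, 29 and 57".

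**Inspection.** Under 6.2 the visual inspection is "conducted periodically from the initial injection until 2 hours after the last injection (minimum", the last word marking two hours as the shortest allowed period. Table 1 schedules inspection at Visits 2, 4 and 5 only. Its row groups inspection with vital signs and blood sampling, and closes by referring to both before and after dosing. Visit 3 has no physical examination. For examinations other than those at screening and early termination, footnote a says: "At all other assessments, physical examinations should only be directed to evaluate reported adverse events".

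**Recording.** Section 6.2: "Any clinically significant findings will be recorded as AEs in the eCRF and in the source documents". It does not define the threshold for injection sites and describes no separate record for other findings. Section 11.1: "An AE is any noxious, unintended, or untoward medical occurrence that may appear or worsen in a subject during the course of a study". The same section has all AEs recorded from consent to the last study visit. Section 11.2.2 grades AEs by CTCAE v4.03, with a fallback scale whose Grade 1 is a mild event needing no treatment.

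**Outputs.** Section 6.5 lists "the incidence and severity of injection site and injection-related reactions (including tryptase and histamine) and treatment-emergent AEs". Section 10.7 lists, as items apart from AEs, "injection site assessments, retinal assessment results, ECG interpretations, and concomitant medications and procedures will be tabulated".

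**AE window.** Section 6.3 and Table 1 footnote d follow AEs for 28 days after the last dose. Section 11.1 runs to the last visit.

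**The concern.** Safety and tolerability is the only secondary objective, and local tolerance of repeated cell injections is an obvious part of it. The instruction that staff follow while looking at the leg is narrower than the general AE rule. A site that follows 6.2 may leave mild redness or swelling unrecorded, while a site that follows 11.1 records it. Both would be complying with the protocol, so the observed rate would depend partly on which section a site applied.

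The filter also reaches further here than for other safety measures. Vital signs and retinal results go into the eCRF whatever they show, and laboratory samples are analysed centrally. For those, a judgement of clinical significance decides only whether the result is also an AE. For injection sites it decides whether the protocol requires any record at all. A table of injection site assessments then lacks a defined source for normal and mild results.

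**Working it through.** **1. Exposure.** Inputs are 15 injections of 0.30 mL (8.2), three dosing days (6.2) and 24 subjects, 8 per arm (10.3).
- Volume per day: 15 × 0.30 = 4.5 mL, which reproduces the stated figure. It also agrees with three syringes of 1.5 mL: 3 × 1.5 = 4.5.
- Injections per subject: 15 × 3 = 45.
- Total: 45 × 24 = 1,080, of which 45 × 16 = 720 are active and 45 × 8 = 360 placebo.

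**2. Recording rules side by side.**

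| Place | What it covers | Severity threshold |
|---|---|---|
| 6.2 | Injection-site inspection findings | Clinically significant, undefined |
| 11.1 | All AEs | None |
| 11.2.2 | Grading of all AEs | Starts at Grade 1 |
| 6.5 | Incidence and severity of site reactions | None stated |
| 10.7 | Injection site assessments, tabulated and summarised as appropriate | None stated |

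Only the first row applies a filter, and it governs the point of observation. The other rows presume data that it does not require.

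**3. Timing of inspections.** Scheduled inspections fall on Days 1, 29 and 57.
- Dose 1 to next inspection: 29 − 1 = 28 days. Visit 3 (Day 15) lies between, with neither a site inspection nor a physical examination.
- Dose 2 to next inspection: 57 − 29 = 28 days.
- Dose 3: no later inspection. The next visit is Visit 6, 93 − 57 = 36 days later.
- The 28-day AE window after dose 3 closes nominally on Day 57 + 28 = 85, before Visit 6.
- Visit windows (Day 57 ± 3, Day 93 ± 7) make the gap between dose 3 and Visit 6 as short as 86 − 60 = 26 days or as long as 100 − 54 = 46. Visit 6 falls inside 28 days only if dose 3 is late and Visit 6 early.

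**4. Size, by illustration only.** The documents give neither a reaction rate nor the share that would be judged clinically significant. Let p be the assumed proportion of subjects with any site reaction and c the assumed share of those subjects recorded. The chance of at least one recorded case in an arm of 8 is 1 − (1 − pc)^8. The expected number among 16 active subjects is 16pc.

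| p | c = 1 | c = 0.5 | c = 0.25 |
|---|---|---|---|
| 10% | 57%; 1.6 | 34%; 0.8 | 18%; 0.4 |
| 25% | 90%; 4 | 66%; 2 | 40%; 1 |
| 50% | 99.6%; 8 | 90%; 4 | 66%; 2 |

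Each cell gives the chance of any case in an 8-subject arm, then the expected active cases. For p = 25%: 1 − 0.75^8 = 0.900 and 1 − 0.875^8 = 0.656. The unit is the subject, because 10.7 counts a subject with a repeated event once.

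**5. Sites.** With about 5 sites (7.1), 24 / 5 is about 5 subjects per site and 8 / 5 = 1.6 per arm per site. One site's reading of the threshold can therefore move a visible part of the observed rate.

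**The case against.** The strongest reply is that 6.2 does not override 11.1. It says that clinically significant findings become AEs; it does not say that the rest go unrecorded. Section 11.1 requires all AEs, 11.2.2 grades mild ones, and Table 1 has AEs assessed at every visit. The separate mention of injection site assessments in 10.7 suggests a dedicated eCRF page, and the eCRF is not among the documents. This stands to the extent that under-counting is a risk and not a certainty. It does not remove the conflict, since no text tells a site which rule governs an inspection finding.

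Several stronger readings are tempting but unsupported:
- A reader might infer that no pre-injection look exists. That follows from 6.2 alone, but the Table 1 row can be read to include one, and 6.2 defers to Table 1. It is an inconsistency.
- A reader might infer that no later visit has an inspection. Visits 4 and 5 do, and the same leg is dosed each time. UENS and NIS-LL at Visits 4 and 6, and distal-leg biopsies at Visit 6, also bring staff to the lower limbs, although these are not site inspections.
- A reader might infer that leftover reactions will be recorded as new. Start and stop dates are required for every AE (11.2.4).
- A reader might infer that 10.7 promises incidence and severity of site reactions. That wording is in 6.5; 10.7 promises tabulation and summary as appropriate.
- A reader might infer bias toward one arm. Investigators and injection staff are blinded, and every arm receives the same number of injections with the same vehicle. The documents give no ground for a directional bias, or for expecting a dose gradient mainly in Grade 1 events.

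**Conclusion.** The point holds as a conflict between recording rules, together with an incomplete inspection schedule. The main defect is that 6.2 is narrower than 11.1 and 11.2.2 and leaves the outputs in 6.5 and 10.7 without a required record of mild or absent findings. The secondary defects are the disagreement between 6.2 and Table 1 on a pre-injection look, the lack of inspection at Visit 3 and after Visit 5, and an AE window in 6.3 and footnote d that conflicts with 11.1 and nominally ends before the first visit after dose 3.

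The amount of under-counting cannot be derived from the documents. The illustrative table rests wholly on assumed rates and recording shares, and on subjects responding independently. It shows only that arms of 8 are sensitive to incomplete recording. Neither the primary endpoint nor the stated power is affected. Label: cheap improvement.

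**What to change.** - **Section 6.2:** require the result of every injection-site inspection, whether a finding or none, to be entered in the eCRF with type and CTCAE v4.03 grade, regardless of judged clinical significance.
- **Section 6.2 and Table 1:** align the two by stating the pre-injection look at Days 1, 29 and 57 explicitly.
- **Table 1:** add a brief visual inspection of the injected area at the existing Visits 3 and 6.
- **Section 6.3, footnote d and 11.1:** reconcile the AE recording period so that reactions after the third dose are captured. Without this, a finding at Visit 6 would usually fall outside the 28-day window and meet conflicting rules.
- **Section 10.7:** tabulate any-grade injection-site reactions by arm and dose number, counted per subject.

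The cost is one more eCRF page and a few minutes at visits that already take place. The tables will show more Grade 1 events. The change concerns data capture and reporting; it does not alter dosing or subject management.
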